Pain Severity	0.69±0.20	0.19-1.00	0%	7%	95%	0.75	0.83
Non-Pain	0.82±0.17	0.32-1.00	0%	22%	87%	0.85	0.83
Psychosocial	0.68±0.17	0.29-0.97	0%	0%	85%	0.92	0.94
Overall HRQOL	0.66±0.18	0.33-0.97	0%	0%	75%	0.92	0.83

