Anticipated Outcome: PFD will have superior QOL and will show improvements in overall QOL over time (≤ 12 months post-operatively) compared to PFDD. In particular, both physical metrics (evaluated by pain frequency, pain severity and non-pain symptoms) and psychosocial metrics will improve at a higher rate and in a shorter period of time after PFD compared to PFDD. QOL will be assessed at the same time points using the Chiari Health Index Pediatrics (CHIP), and the Health Utilities-3 (HUI-3). For this aim, CHIP QOL (≤ 12 months post-operatively) will be used as the primary outcome, and HUI-3 and the domain sub-scores presented below will be assessed as the secondary outcomes. Additional, sensitivity analyses will be performed for the CHIP QOL based on the last reported CHIP QOL scores including up to 24 months post-operatively.

Corresponding Metrics for QOL:

Assumptions on dates and times were based on the following:

- Assuming 1 Month = 30 days
- From protocol, we wish to report CHIP assessments are at baseline, within 6 weeks of surgery, within 3-6 months of surgery and within 12 +/- 2 months of surgery.
- CHIP QOL was calculated via the method described in: https://thejns.org/pediatrics/view/journals/j-neurosurg-pediatr/17/1/article-p76.xml
- Only patients with complete entries were considered in the report.
- Domain sub-scores (sums of indicators) for each of the following domains of CHIP:
 - Pain Frequency
 - o Pain Severity
 - Non-Pain Symptoms
 - Psychosocial/Cognitive
- Overall QoL outcome (non-uniform weighted avg.) of the above 4 domains

2. STUDY DESIGN

This will be a cluster randomized control trial of 148 patients recruited from the 36 centers of the Park-Reeves Syringomyelia Research Consortium (PRSRC) as well as an additional 7 research centers. Randomization will occur at the center level with standardized surgical technique, and data will be recorded in the PRSRC prospective registry. In order to examine the main comparative effectiveness research (CER) question of surgical complications and potential harm to patients

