It should be noted that it is assumed that the average cluster size is 6 in all centers for these calculations. The design effect (DE) concept is used in cluster randomized trials to inflate the sample size of the study, compared to the traditional randomized trials [44]. When cluster size is fixed, $DE = 1 + [(m - 1) \times ICC]$; where m is the average cluster size and ICC is the intraclass correlation coefficient. In other words, the sample size of the study can be calculated by traditional methods, and should be multiplied by the DE. Under the assumption that m = 6 and ICC = 0.01, DE becomes 1.05. To compare 17.8% vs 2.7% surgical complication rates for a (*not clustered*) randomized trial, with 84% power, and 0.05 type I error rate, we would need to enroll 136 patients total. This is also listed in the sample size calculator above under the "unadjusted box". For a DE value of 1.05, this sample size should be multiplied by 1.05 to find the sample size of a cluster randomized trial to reach same power. Therefore, the sample size of the clustered randomized trial would be 136 x 1.05 = 142.8 ~143.

The variable cluster size is common in cluster randomized trials. Eldridge et al considered the effect of variable cluster size on the sample size calculation for cluster randomized trials [45]. They showed that the DE value can be calculated for variable class sizes. DE' = $1 + {(cv^2+1) m - 1} x$ ICC; where cv is the coefficient of variation of cluster sizes (standard deviation of cluster sizes divided by the mean cluster size). The cv is 1.08 for our study. If we use the current average cluster size of m = 2.9, DE' becomes 1.06. In other words, the sample size of the study should be inflated to 136 x 1.06 = 144.16~145 to reach 84% power. This assures us that our planned sample size of 145 patients will allow us to reach 84% power even if our cluster sizes will not be fixed at 6.

It should be noted that, as of March 6th 2018, only 1 of 100 enrolled patients was lost to followup. However, to account for a potential 2% loss to follow up on the 145 subjects needed (72 per group), we will recruit 148 subjects total (74 per group) over the entire trial enrollment period, which is proposed to be extended to December 31, 2018.

Aim 2: Non-Inferiority Margins and Power

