recommended non-inferiority margin of 0.175 units for the clinical improvement outcome is consistent with the FDA-recommended largest acceptable non-inferiority margin of 0.175 units.

In contrast to clinical improvement, syrinx regression is an objectively measurable and easily quantifiable outcome. It is measured by comparing syrinx size on MRI scans obtained before and after surgery. When the effective sample size is 68 subjects per group, and assuming 89.1% syrinx regression rate in the PFDD group [27], the non-inferiority margin is 0.135 units to reach 81% power. A non-inferiority margin of 0.135 units represents no more than 13.5% reduction from the PFDD group in terms of syrinx regression. Note that a one-sided type I error rate of 0.05 was assumed, and the 'Two group test of equivalence in proportions' option in nQuery Advisor was used for the sample size calculations.

Determine if PFD provides non-inferior syrinx regression compared to PFDD (Non-inferiority Design)							
Outcome	PFDD	PFD	Data Source	Non-inferiority Margin	α-level	Subjects per group	Power
Syrinx Regression	261/293 (89.1%)	31/38 (81.2%)	Durham [27] and PRSRC	0.135	0.05	72	81%

For these calculations, the drop-out rate is assumed to be 2%, intra-class correlation coefficient is 0.05, and the onesided type I error rate is 0.05.

Aim 3: Power Calculations

Based on preliminary data using the Chiari Health Index in Pediatrics (CHIP)[50], we observed a 0.12±0.16 unit improvement in Quality of Life (QOL) scores following PFDD. Our sample size of 72/group (effective sample size of 68/group) will provide 82% power to detect a 0.20±0.16 unit improvement in CHIP QOL scores following PFD (α =0.05). Both from an analytical standpoint and from the view of PRSRC investigators and our patient partners, this value represents both a significant and meaningful increase in QOL

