Sub-analysis by Syrinx size (3-6 mm, 7-9 mm): A planned subgroup analysis for each of the 3 to 6 mm and 7 to 9 mm syrinx diameters will be performed for each of the 3 aims. The test of interaction will be used to assess if the treatment effect is homogeneous within each of the syrinx size subgroups (3- 6 mm vs 7-9 mm). If the test of interaction indicates heterogeneity, using the whole 3 to 9 mm syrinx diameter range, analyses will be performed, to identify, if any, a cut-off point to propose using one surgical method over the other. For example, whether the PFD is associated with greatly fewer surgical complications when the syrinx diameter is less than 5mm, but surgical complication rates are similar for PFD and PFDD when the syrinx diameter is \geq 6 mm will be examined.

Secondary Analysis

The aims will be evaluated using the overall population who were followed from 6 months to 24 months after enrollment. Analysis will be performed to compare the per Treatment groups for time to last follow-up in order to determine if there is differential follow-up times between groups. Analysis of Aims 2 and 3 will be similar to the primary analysis with adjustment for time to last follow-up as a covariate.

Aim 3 includes some questions that may not be applicable for younger children. For example, keeping up with schoolwork or difficulty with math. Therefore, for this ,a subgroup analysis for

those children age >5 years will also be performed. Additional analysis will include subdomain comparisons of: Pain symptoms Headache Back pain Non-pain symptoms Difficulty raising arms Difficulty walking Frequently lose balance Psychosocial Tired Easily frustrated Trouble sleeping Difficulty concentrating Difficulty paying attention in class Forgetful Difficulty with reading Difficulty with math Difficulty learning new things Difficulty keeping up with schoolwork. Covariates in this analysis will include medical history (Autism, ADHD, Known Psych Disease),

pathology (known Craniofacial Anomalies, Known Skull Malformation, Known Hydrocephalus, Known Spine Column Disorder) and Syrinx (Syrinx Level Known, Syrinx AP Diameter).

Exploratory Analysis

Additional exploratory subgroup analyses will be performed for Aims 2 and 3. These analyses will include age (<5,5-12,13-18), CM status (5-12,>12 mm), and preoperative hydrocephalus or neuromuscular disease. These analyses will examine if there is differential response between the groups.

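### SAP limits the CHIP analysis to complete forms, but the Aim 3 power of 82% allows nothing for incomplete ones; at the 75% completeness in the protocol's Table 4 it would be about 71%

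*SAP*

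**What the plan says.** - **Completeness rule.** SAP 1.2, Specific Aim 3, makes CHIP the primary outcome of that aim. Among the scoring notes it says: "Only patients with complete entries were considered in the report". The same notes define domain sub-scores as sums and the overall score as a weighted average of the four domains, and refer to a published article for the method. They give no rule for an unanswered or not-applicable item.
- **Completeness of the instrument.** In Protocol 7.2.1, Table 4, the row "Overall HRQOL" shows 75% complete. The physical and psychosocial rows show 84% and 85%.
- **Power.** SAP 7.2.1 (repeated in Protocol 9.5) starts from this: "we observed a 0.12±0.16 unit improvement in Quality of Life (QOL) scores following PFDD". The sample size is "72/group (effective sample size of 68/group", which the SAP says "will provide 82% power to detect a 0.20±0.16 unit improvement in CHIP QOL scores following PFD". The only allowance for lost data is "to account for a potential 2% loss to follow up on the 145 subjects needed (72 per group".
- **Missing data.** SAP 7.5 bases the primary Aim 3 analysis on the 10 to 14 month visit. It plans a linear mixed model with a random centre effect, and imputation by last observation carried forward and by Buck's method.
- **Young children.** SAP 7.5, Secondary Analysis: "Aim 3 includes some questions that may not be applicable for younger children". It adds an analysis restricted to children over 5. Eligibility has an upper age limit of 21 and no lower limit.

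**The concern.** As written, the rule discards every CHIP form with a gap, however small, from the primary analysis of a named aim. The sample size was set as if nearly every followed patient would yield a score. The only completeness figure for the overall score in the documents suggests that a quarter of forms might not.

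The rule also disagrees with the plan's own missing-data section. SAP 1.2 excludes incomplete forms, while SAP 7.5 imputes missing data and fits a model meant to use all available visits. Two analysts following the same SAP could therefore analyse different sets of patients. At stake are the power of Aim 3 and a clear definition of which patients its result describes.

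**Working it through.** **Inputs.** Mean improvement is 0.12 (PFDD) and 0.20 (PFD), so the difference is 0.08. The SD is 0.16, effective n is 68 per group and α is 0.05 (all SAP 7.2.1, Aim 3). The SAP does not state sidedness for Aim 3. Completeness rates come from Protocol Table 4.

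**Step 1: reproduce the stated figure.** For two means with n per group,

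power = Φ( (δ/σ)·√(n/2) − 1.96 ), with δ/σ = 0.08/0.16 = 0.5.

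At n = 68: 0.5 × √34 − 1.96 = 2.916 − 1.96 = 0.956, and Φ(0.956) = 83.0%. The two-sample t-test gives 82.5%. The stated 82% is therefore a two-sided figure at effective n = 68. A one-sided test would give 89.8%, and n = 72 without a design effect 85.1%. The reduction from 72 to 68 is a design effect of 72/68 = 1.06. The 72 is already net of the 2% loss from 74, so nothing remains for incomplete forms.

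**Step 2: apply the complete-entries rule.** Multiply 68 by the completeness rate and recompute.

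| Completeness | Source | Effective n per group | Power (normal) | Power (t-test) |
|---|---|---|---|---|
| 100% | implied by the plan | 68 | 83.0% | 82.5% |
| 90% | illustration | 61.2 | 79.0% | 78.3% |
| 85% | Table 4, psychosocial | 57.8 | 76.7% | 76.0% |
| 84% | Table 4, physical | 57.1 | 76.2% | 75.5% |
| 75% | Table 4, overall | 51 | 71.4% | 70.6% |

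For the last row: 0.5 × √25.5 − 1.96 = 2.525 − 1.96 = 0.565, and Φ(0.565) = 71.4%.

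**Step 3: check sensitivity to the design effect.** Fewer usable forms per centre slightly reduce the clustering penalty. With 6 × 0.75 = 4.5 forms per centre and an ICC of 0.01, the design effect is 1 + 3.5 × 0.01 = 1.035. Effective n is then 54/1.035 = 52.2 and power 72.4%. With no design effect (n = 54), power is 73.8%. The conclusion does not change.

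**Step 4: completeness needed for 82%.** n = 2 × ((1.96 + 0.915)/0.5)² = 66.1, and 66.1/68 = 97%. The t-test needs slightly more, so the requirement is about 97–98%. Conversely, at 75% complete, 72/0.75 = 96 followed patients per group would be needed to restore an effective 68. With 51 per group, the difference detectable with 82% power rises from about 0.08 to 0.16 × √(2/51) × (1.96 + 0.915) = 0.091.

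**Step 5: can the planned imputation repair the gap?** Last observation carried forward uses an earlier form, which may lack the same items. Buck's method, as specified, predicts from age, tonsillar ectopia, syrinx diameter and comorbidities, not from the CHIP items that were answered. The mixed model can use a visit only if its form yields a score, and under the rule a partly answered form yields none.

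**The case against.** The strongest reply is that the quoted line is in the past tense, refers to a report and sits under a list of date assumptions. The forward-looking plan in SAP 7.5 already contains a mixed model, imputation, and sensitivity analyses using later CHIP visits. This has some force: the reach of the line is unclear. But SAP 1.2 writes other operative scoring rules in the past tense too, including the binary symptom scoring, and the line stands among the CHIP scoring rules with no other completeness rule in the document. If it was not meant to govern the primary analysis, the SAP should say so.

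Second, the 82% is arithmetically sound, and 75% comes from development data rather than from the trial. That stands, so the lower power figures are conditional.

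Third, the protocol allows up to 238 patients. At 119 per group with 2% loss, the same design effect and 75% completeness, effective n is 119 × 0.98 × (68/72) × 0.75 = 82.6 and power is about 89%. The SAP, however, fixes enrolment at 148.

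Fourth, a reader might infer that the rule systematically removes the youngest children and empties the under-5 subgroup. The documents do not show this. Nowhere do they say that a not-applicable item makes a form incomplete, and Protocol 7.2.1 lets a parent complete the form alone. The SAP plans an under-5 subgroup for Aim 3, so its authors expect scores at that age. Nor does Table 4 place the gaps in the school items: the psychosocial domain, with 24 items, is 85% complete, against 84% for the physical items. Disproportionate loss of young children remains possible, no more.

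**Conclusion.** The concern holds in conditional form. A stated rule, followed as written, discards partly answered CHIP forms. The Aim 3 power makes no allowance for this, and the rule conflicts with the missing-data plan in SAP 7.5. If Table 4 completeness applied at the 10 to 14 month visit, power would be about 71% at the overall rate and 76–77% at the domain rates, against 82% stated. This assumes the plan's own difference and SD, a two-sided test, and a design effect close to 1.06.

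Two stronger readings are not supported. A reader might infer that the arm comparison is biased. The same rule applies in both arms, and nothing in the documents shows loss that differs by arm or depends on outcome. A reader might also multiply baseline and 12-month completeness as if they were independent and arrive at a much lower power. The documents give no basis for independence, and gaps caused by a child's age would tend to recur at both visits.

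**What to change.** 1. Replace the complete-entries rule for the primary Aim 3 analysis so that partly answered forms contribute. Define a complete form, and say how not-applicable and unanswered items are scored: by the instrument's published missing-item rule or, if it has none, by a pre-specified pro-rating rule.
2. Handle forms that still cannot be scored through the mixed model already planned, or by multiple imputation that uses the answered CHIP items. Make SAP 1.2 and SAP 7.5 agree.
3. Keep the complete-form analysis as a sensitivity analysis.
4. Report completeness by arm and by age group.
5. Restate Aim 3 power as conditional on the usable-form rate, for example with the table above.

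The cost is SAP wording and modest programming. Pro-rated scores are slightly noisier than complete ones and may depart from the published scoring, which the retained complete-form analysis would help to reveal. Restating power does not enlarge the sample, but it tells readers how to weigh a null result for Aim 3.

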3.1 Inclusion Criteria

- 1) Age ≤ 21 years old
- 2) Chiari malformation type I with \geq 5 mm tonsillar ectopia
- 3) Syrinx diameter (recorded as the greatest antero-posterior or transverse diameter) 3-9 mm
- 4) MRI of the brain and cervical and thoracic spine are required prior to surgery and available to be shared with the DCC

3.2 Exclusion Criteria

- 1) Syrinx $<3 \text{ mm and/or} \ge 10 \text{ mm}$
- Neuro-imaging demonstrating basilar invagination (position of the superior tip of dens ≥5 mm above Chamberlain's line)
- 3) Neuro-imaging demonstrating clival canal angle <120°
- 4) Prior PFD, PFDD, or other surgery at the craniovertebral junction
- 5) CM+SM secondary to other pathology (e.g. a tumor)
- 6) Unable to share pre-decompression MRI of the brain and cervical and thoracic spine
- 7) Patients who do not wish to participate.

4.6 Randomization and Treatment Allocation

A cluster randomized controlled trial (C-RCT) will be conducted to compare the two major neurosurgical treatments for CM+SM, PFDD and PFD. The cluster size is expected to be on average 6 participants per center (~3 per center per year). In order to participate, PRSRC centers with multiple pediatric neurosurgeons were given the option of complying with the treatment allocation and following a standardized procedure or selecting a single study neurosurgeon for the group. If the latter scenario was chosen, the group had to agree that all CM+SM patients referred to that center must be treated by the study neurosurgeon. For cluster randomization, a computer-generated randomization sequence will be generated independently by the study statistician. All eligible participants within each cluster will then be approached for informed consent for the purposes of data collection for the trial.

4. STUDY INTERVENTIONS

4.1 Interventions, Administration, and Duration

The intervention performed will either be a PFD or PFDD. It will be predetermined, based on cluster randomization, which procedure each center performs on their respective participants. A computer-generated randomization sequence will be generated independently by the study statistician. The surgery will occur in each respective center's operating room. With the exception of uniformly receiving the designated center intervention, all research participants will receive usual clinical care in accordance with institutional practice and judgment. Clinical care will include at a minimum an initial clinical evaluation by a participating pediatric neurosurgeon, surgical treatment (PFDD or PFD) and associated perioperative care, and routine post-operative care with prescribed follow-up clinical assessments at ≤ 6 weeks, 3-6 months, and 12 months (+/-2 months = 10-14 months) after surgery

4.2 Concomitant Interventions

4.2.1 Allowed Interventions

Medications or other treatments may be administered per usual institutional clinical practice. PFD or PFDD must follow the procedural guidelines outlined in this protocol.

4.2.2 Required Interventions

There are no required interventions outside of the PFD or PFDD procedure itself.

4.2.3 Prohibited Interventions

PFD or PFDD must be in accordance with the procedural guidelines outlined in this protocol. For the purposes of this study, PFD performed with dural opening but no dural closure is not permitted. Similarly, cases requiring concomitant cervical or occipito-cervical fusion or upfront direct syrinx surgery (syrinx fenestration or shunt) are not permitted.

4.3 Adherence Assessment

Periodic quality assurance checks will be performed primarily via remote monitoring by reviewing a random subset of operative notes at each participating site.

5. STUDY PROCEDURES

5.1 Schedule of Evaluation

Assessment	Initial Visit	<6 Weeks Follow-Up Visit	3-6 Month Follow-up Visit	12 Month Follow- up Visit
Inclusion/Exclusion Criteria	Х			
Cluster Randomization	Х			
Informed Consent Form	Х			
Demographics	Х			
Presenting Symptoms	Х			
Childhood History	Х			
Developmental History	Х			
Allergies	Х			

Concomitant Medications	Х			
Family History	Х			
Social History	Х			
General Exam	Х			
Musculoskeletal Exam	Х			
Initial Radiology	Х			
Diagnosis	Х			
Clinical Course of Treatment	Х	Х	Х	Х
Complications	Х	Х	Х	Х
Pt Status	Х	Х	Х	Х
CHIP	Х	Х	Х	Х
HUI-3 QOL	Х	Х	Х	Х
Follow-up Symptoms		Х	Х	Х
Follow-up Medications		Х	Х	Х
Follow-up General Exam		Х	Х	Х
Follow-up Neurological		Х	Х	Х
Exam				
Follow-up Musculoskeletal		Х	Х	Х
Exam				
Follow-up Radiology		^	^	Х
Additional		Х	Х	Х
Neurological/Orthopedic				
Exam				

^ Any subsequent pre-operative images (Brain/spine MRI/CT/X-rays) will be shared, including in the following scenarios:

- Revision/redo decompression
- Syrinx shunt or fenestration
- Spinal Fusion

5.2 Adverse Events and Serious Adverse Events

SAFETY ASSESSMENTS

Complications will be recorded at the following time points:

- Intra-operatively
- $\circ \leq 6$ months after initial PFD or PFDD
- 6-12±2 months after initial PFD or PFDD

The following definitions are provided for clarification:

- Pseudomeningocele: an extradural and/or subcutaneous fluid collection resulting in discomfort or pain, limitation of movement, or CSF leak. Radiological evidence of fluid collection alone is not sufficient for diagnosis of pseudomeningocele.
- Hydrocephalus: requires external drainage, shunting, or endoscopic 3rd ventriculostomy.
- Infection: clinical diagnosis that may include fever, wound drainage, dehiscence, or elevated laboratory parameters in association with antibiotic treatment ± surgical debridement.
- Chemical (or aseptic) meningitis: clinical diagnosis prompting medical treatment (e.g. steroids); lumbar puncture and analysis of CSF cell profile not required but

will be tracked if available.

• True meningitis: lumbar puncture and positive cultures required.

Known potential complications include the following:

- Intra-operatively
 - Vascular injury
 - Hemorrhage requiring evacuation
 - Neurologic Injury
 - Cranial nerve injury or palsy
 - Weakness
 - Sensory Changes
 - Bowel Dysfunction
 - Bladder Dysfunction
 - Death
- Complications \leq 6 months or 6-12 \pm 2 months after PFD or PFDD
 - Pseudomeningocele: Form 16402 (4), ChiariPOPseudomen
 - CSF leak: Form 16634 (10), ChiariPOCSFLeak
 - Hydrocephalus: Form 16427 (6), Hydrocephalus
 - Infection: Form 16416 (5), ChiariPOWRInfection
 - Aseptic meningitis: Form 16420 (5), ChiariPOchemicalMeningitis
 - True meningitis: Form 16416 (5), ChiariPOTrueMeningitis
 - Cervical Instability: Form 16431 (6), CervicalInstability

Possible interventions for known complications are as follows:

- Intra-operative complications
 - Evacuation of hemorrhage
 - Open or endovascular repair vascular injury
- $\circ \leq 6$ month or 6-12 ± 2 month postoperative complications
 - Hydrocephalus
 - External ventricular or lumbar drain placement
 - Implantation of ventriculo-peritoneal or other permanent shunt
 - Endoscopic 3rd ventriculostomy for hydrocephalus
 - CSF leak:
 - Over-sewing of wound
 - External ventricular or lumbar drain placement
 - Surgical revision in the operating room
 - Pseudomeningocele
 - Percutaneous drainage
 - External ventricular or lumbar drain placement
 - Surgical revision in the operating room
 - Infection
 - Bedside debridement
 - Surgical revision in the operating room.
 - Shunt malfunction/infection
 - External ventricular or lumbar drain placement

- Shunt externalization or removal with or without external ventricular or lumbar drain placement
- Shunt revision in the operating room
- Chemical meningitis
 - Lumbar puncture
 - Steroids
- Bacterial meningitis
 - Lumbar puncture
 - IV antibiotics
- Cervical instability
 - External orthosis (e.g. cervical collar, halo vest)
 - Surgical fusion
- Cerebellar ptosis
 - Cerebellopexy

Separate from these complications, other unexpected complications that are related to the surgery and other adverse events that occur that are not related to the surgery will be recorded for the < 6 month and 6-12 (+/- 2 months) month time intervals. Such events will be reported by site investigators.

Specification of Safety Parameters

The presence of any of the following items will be considered as a harm to patients.

• Intra-operative Complication

- Vascular injury resulting in dissection or stroke. Dissection will be diagnosed via angiographic imaging (CT angiogram, MR angiogram, catheter angiogram) and stroke via CT or MRI imaging.
- Intracranial hemorrhage requiring return to surgery for evacuation
- Neurological injury resulting in:
 - Cranial nerve deficit
 - New weakness
 - Sensory loss
 - Bowel or bladder dysfunction
- o Death
- Complications \leq 6 months after PFD or PFDD

See definitions above.

- Pseudomeningocele
 - CSF Leak
 - Hydrocephalus
 - Infection
 - Chemical (or aseptic) meningitis
 - Bacterial meningitis
 - Cervical instability
 - Cerebellar ptosis with intractable headaches
- Interventions for complication management <6 months after initial PFDD or PFD

- Hydrocephalus
 - External ventricular or lumbar drain placement
 - > Implantation of ventriculo-peritoneal or other permanent shunt
 - Endoscopic 3rd ventriculostomy for hydrocephalus
- CSF leak:
 - Over-sewing of wound
 - > External ventricular or lumbar drain placement
 - Surgical revision in the operating room
- Pseudomeningocele
 - Percutaneous drainage
 - > External ventricular or lumbar drain placement
 - Surgical revision in the operating room
- Infection
 - Bedside debridement
 - Surgical revision in the operating room.
- Shunt malfunction/infection
 - > External ventricular or lumbar drain placement
 - Shunt externalization or removal with or without external ventricular or lumbar drain placement
 - > Shunt revision in the operating room
- Chemical meningitis
 - Lumbar puncture
 - > Steroids
- Bacterial meningitis
 - Lumbar puncture
 - > IV antibiotics
- Cervical instability
 - External orthosis (e.g. cervical collar, halo vest)
 - Surgical fusion
- Cerebellar ptosis
 - Cerebellopexy

• Complication 6-12 (+/- 2 months) months after initial PFDD or PFD

- o Pseudomeningocele
- CSF leak
- Hydrocephalus
- o Infection
- Chemical (or aseptic) meningitis
- Bacterial meningitis
- o Cervical instability
- Interventions for complication management 6-12 (+/-2 months) months after initial PFDD or PFD
 - Hydrocephalus
 - External ventricular or lumbar drain placement
 - > Implantation of ventriculo-peritoneal or other permanent shunt

- Endoscopic 3rd ventriculostomy for hydrocephalus
- CSF leak:
 - Over-sewing of wound
 - > External ventricular or lumbar drain placement
 - Surgical revision in the operating room
- Pseudomeningocele
 - Percutaneous drainage
 - > External ventricular or lumbar drain placement
 - Surgical revision in the operating room
- Infection
 - Bedside debridement
 - Surgical revision in the operating room
- Shunt malfunction/infection
 - > External ventricular or lumbar drain placement
 - Shunt externalization or removal with or without external ventricular or lumbar drain placement
 - Shunt revision in the operating room
- Chemical meningitis
 - Lumbar puncture
 - > Steroids
- Bacterial meningitis
 - Lumbar puncture
 - > IV antibiotics
- Cervical instability
 - External orthosis (e.g. cervical collar, halo vest)
 - ➢ Surgical fusion
- Cerebellar ptosis
 - ➢ Cerebellopexy

Adverse Events and Serious Adverse Events

Adverse Event Reporting

All adverse events will be evaluated as to whether their occurrence was expected or unexpected. For this study, *expected* AEs include the following common surgical complications (*see above for definitions*):

- Pseudomeningocele
- CSF leak
- Infection
- Chemical meningitis
- Bacterial meningitis
- Hydrocephalus
- Need for surgical procedure for complication management
 - Oversewing of wound
 - Bedside debridement
 - Surgical revision in the operating room
 - External ventricular or lumbar drain placement
 - Implantation of ventriculo-peritoneal or other permanent shunt
 - Endoscopic third ventriculostomy for hydrocephalus

• Shunt revision in the operating room

Unexpected AEs will include uncommon surgical complications and AEs which may be unrelated to the study intervention:

- Clinically significant intracranial hemorrhage
- Skull fracture
- Positioning/pressure sores
- Cerebellar ptosis with intractable headaches
- Cervical instability
- Urinary tract infection
- Need for surgical procedure for complication management
 - Evacuation of hematoma
 - Cerebellopexy for cerebellar ptosis
 - Cervical or occipital-cervical fusion
- Deep venous thrombosis
- Unsolicited complications related to decompression surgery
- Unsolicited complications not related to decompression surgery

Data Collection Procedures for Adverse Events

After enrollment, AEs, whether expected or unexpected, will be recorded according to the date of first occurrence, severity, duration, and any treatment prescribed. Any medical condition present at the time of enrollment, which remains unchanged or improved, will not be recorded as an adverse event on the Adverse Events Log. All study subjects will be monitored for adverse events from the time of enrollment until the time of discharge from the hospital and at each follow-up evaluation. Adverse events for subjects who withdraw from the study will be monitored and reported until the point of study withdrawal.

Serious Adverse Events

Serious adverse events (SAEs) will be defined as untoward medical occurrences that result in a life-threatening change of condition, require further inpatient hospitalization, or result in persistent or significant disability/incapacity or death. In the current study, SAEs will include the following:

- Intra-operative vascular injury or stroke
- Neurological injury (cranial nerve deficit, new weakness, sensory loss, bowel or bladder dysfunction)
- Visceral injury
- Pulmonary embolism
- Pneumothorax
- Need for unexpected re-intubation
- Cardiopulmonary arrest
- Death
- Unsolicited SAEs related to decompression surgery

Unsolicited SAEs not related to decompression surgery

